5.2 EXCLUSION CRITERIA

An individual who meets any of the following criteria will be excluded from participation in this study:

1. Clinically significant abnormalities on EKG or laboratory testing. This includes CBC; acute care panel (Na, K, Cl, CO₂, creatinine, glucose, urea nitrogen); hepatic panel (alkaline phosphatase, ALT, AST, bilirubin total, and bilirubin direct); mineral panel (albumin, calcium, magnesium, phosphorus); prothrombin and partial prothrombin tests.
2. Participants should not have taken NSAIDs or willow bark tea for two weeks prior to the PET scan.
3. Any current Axis I diagnosis.
4. Positive test for HIV.
5. Unable to have an MRI scan*.
6. History of neurologic illness or injury with the potential to affect study data interpretation.
7. History of seizures, other than in childhood and related to fever.
8. Recent exposure to radiation (i.e., PET from other research) which when combined with this study would be above the allowable limits.
9. Inability to lie flat on camera bed for at least two hours, including claustrophobia and weight greater than the maximum for the scanner (500 lbs).
10. Pregnancy or breast feeding.
11. Able to get pregnant but does not use birth control.
12. Participants must not have substance use disorder or alcohol use disorder. However, alcohol or cannabis use by themselves are not exclusion criteria, unless that use affects the function of daily life.
13. Unable to travel to NIH.
14. NIMH staff or an NIH employee who is a subordinate/relative/co-worker of the investigators.

*Phase 1 and 3 participants will not get an MRI.

5.2.1 Exclusion of Children

Because this protocol has more than minimal risk from radiation exposure without possibility of direct benefit, inclusion of children is not appropriate.

5.2.2 Exclusion of Pregnant or Breastfeeding Women

Pregnant women will be excluded because this protocol involves exposure to ionizing radiation. Lactating women will be excluded because radioisotopes may be excreted in milk.

5.2.3 Exclusion of Participants who are HIV Positive

Persons with HIV infection are excluded because HIV infection itself may change cAMP signaling.

Abbreviated Title: [¹⁸F]SF12051 in Healthy Subjects

Version Date: 12/05/23

5.3 INCLUSION OF VULNERABLE PARTICIPANTS

5.3.1 Participation of NIH Staff or family members of study team members

NIH staff may be enrolled in this study as the population meets the study entry criteria and NIH Policy 404 will be followed. There will be no direct solicitation of NIH employees, nor will they be directly recruited by or through their supervisors or co-workers to participate in this study. Neither participation nor refusal to participate as a subject in the research will have an effect, either beneficial or adverse, on the participant's employment or position at NIH. NIH employees must have permission from their supervisor and/or take leave in order to receive compensation if participation is during work hours. Prior to enrollment, the NIH employee will be requested to review the Annual Leave Policy for NIH Employees. Participant confidentiality and privacy will strictly be held in trust by the participating investigators, their staff, and the sponsor(s).

Per NIMH Policy, NIMH employees, staff and their immediate family members will be excluded from the study due to ethical concerns about confidentiality and conflict of interest. A copy of the ““NIH Frequently Asked Questions (FAQs) for Staff Who are Considering Participation in NIH Research” will be made available for NIH employees who wish to participate in this study.

5.4 LIFESTYLE CONSIDERATIONS

During this study, participants are asked to:

- Abstain from strenuous exercise and from lifting more than 10 pounds using the affected arm for 48 hours after removal of the arterial line.
- Abstain from taking NSAID pain medication for 2 weeks prior to the PET scan visit(s). If subject is experiencing pain, they can take Tylenol and still be eligible for the study.

5.5 SCREEN FAILURES

Screen failures are defined as participants who consent to participate in the clinical trial but are not subsequently assigned to the study intervention or entered in the study. A minimal set of screen failure information is required to ensure transparent reporting of screen failure participants, to meet the Consolidated Standards of Reporting Trials (CONSORT) publishing requirements and to respond to queries from regulatory authorities. Minimal information includes demography, screen failure details, eligibility criteria, and any serious adverse event (SAE).

5.6 STRATEGIES FOR RECRUITMENT AND RETENTION

Healthy volunteers will be recruited from protocol # 01M0254.

Flyers (with tear offs) may be posted on NIH bulletin boards, at coffee shops, grocery stores, community centers, bookstores, NIH Clinical Center, libraries or placed in doctor's office waiting rooms, retail establishments as well as on public transportation vehicles and/or bus shelters/train stations may be used (all with permission and according to the guidelines of the facility) or sent electronically (without tear offs) to those who request a copy.

Recruitment will also include use of Research Match, Listservs, Craig's List, advocacy websites, resource listings or other website postings and Study-specific page on the NIMH-IRP:

Abbreviated Title: [¹⁸F]SF12051 in Healthy Subjects

Version Date: 12/05/23

Join A Study Website with URL (placeholder). Short text descriptions of this study will also appear on Facebook. Facebook posts will be made only via official NIMH accounts.

Brochures and other IRB-approved recruitment materials or study information may be given directly to individuals interested in our research in both hard copy and electronic formats, depending on request. Associate Investigators and members of the NIMH Marketing & Community Relations Unit will distribute recruitment materials to individuals/groups, such as mental health clinics, hospitals, self-help and advocacy groups, and local clinicians. Clinicians who are contacted will be provided with information to disseminate to patients as they see fit. We will explain to them that individuals interested in participating in our studies will need to initiate contact with our group and that we will not make this initial contact.

The protocol and contact information to obtain further details will be listed on www.clinicaltrials.gov.

5.6.1 Costs

We expect participants to incur no costs for participating in this study.

5.6.2 Compensation

Participants will be compensated for time- and research-related inconveniences. Reimbursement is based on NIH standards for time devoted to the research project. Participants will be paid for each portion of the study they complete whether or not they opt for early withdrawal from participation. Without incomplete study procedures or unanticipated inconvenience, the total possible compensation for procedures is \$220 for Phases 1 and 3, \$390 for Phase 2, and \$650 for Phase 4. These compensation amounts do not account for time spent at the NIH, for which the first hour of each visit is compensated \$20 and every subsequent hour is compensated \$10. Payment will be submitted after completion of each visit to NIH through direct deposit. If the investigators need to delay study procedures or if additional time is need for completion, participants may receive additional compensation in accordance with NIH guidelines.

Due to last-minute cancellations, appointments may be scheduled within 72 hours' notice. Participants who are scheduled for appointments on short notice may be eligible for a bonus payment of \$250 if they are scheduled and complete a visit with less than 72 hours' notice.

Outpatient participants will receive support for travel, meals, and lodging according to NIH travel policy guidelines. Lodging may be provided directly or reimbursed according to NIH guidelines. Employees and staff who participate during work hours must have permission from their supervisor. NIH employees must either participate outside of work hours or take leave in order to receive compensation.

Subjects undergoing Dosimetry Whole-body Scan (Phases 1 and 3)

| | |
|-----------------------|-------|
| Visit 1 to NIH | |
| Screening | \$20 |
| Pregnancy test | \$10 |
| Visit 2 to NIH | |
| PET scanning | \$150 |

Abbreviated Title: [¹⁸F]SF12051 in Healthy Subjects

Version Date: 12/05/23

| | |
|------------------------------|---------------|
| Antecubital venous catheters | \$30 |
| Pregnancy test | \$10 |
| Movement restriction | \$10 |
| Total | \$230* |

Subjects undergoing Brain Scan (Phase 2)

| | |
|------------------------------|---------------|
| Visit 1 to NIH | |
| Screening | \$20 |
| Pregnancy test | \$10 |
| Visit 2 to NIH | |
| PET scanning | \$150 |
| Arterial catheter | \$60 |
| Antecubital venous catheters | \$30 |
| Pregnancy test | \$10 |
| Movement restriction | \$10 |
| Visit 3 to NIH | |
| Brain MRI | \$100 |
| Pregnancy test | \$10 |
| Total | \$400* |

Subjects undergoing Test-Retest Brain Scans (Phase 4)

| | |
|------------------------------|---------------|
| Visit 1 to NIH | |
| Screening | \$20 |
| Pregnancy test | \$10 |
| Visit 2 to NIH | |
| PET scanning | \$150 |
| Arterial catheter | \$60 |
| Antecubital venous catheters | \$30 |
| Pregnancy test | \$10 |
| Movement restriction | \$10 |
| Visit 3 to NIH | |
| PET scanning | \$150 |
| Arterial catheter | \$60 |
| Antecubital venous catheters | \$30 |
| Pregnancy test | \$10 |
| Movement restriction | \$10 |
| Visit 4 to NIH | |
| Brain MRI | \$100 |
| Pregnancy Test | \$10 |
| Total | \$660* |

* Participants are eligible for a \$250 bonus payment if they were scheduled and completed a PET visit within 72 hours' notice.

Abbreviated Title: [¹⁸F]SF12051 in Healthy Subjects

Version Date: 12/05/23

6 STUDY INTERVENTION

6.1 STUDY INTERVENTIONS(S) ADMINISTRATION

6.1.1 Study Intervention Description

Each participant will receive an injection of [¹⁸F]SF12051 during each PET scan.

6.1.2 Dosing and Administration

Each participant will be intravenously injected with about 5 mCi of [¹⁸F]SF12051 for each PET scan. The yield of the radioligand synthesis varies such that the available dose may be < 5 mCi. By prior agreement with NIH's Radiation Safety Committee, the clinician covering the scan can approve a dose as low as half of the prescribed dose. We expect that a dose of 2.5-5 mCi will likely be adequate for all participants. The maximal dose will provide the best accuracy to measure radioactivity in brain with PET and the parent radioligand in plasma with radioHPLC.

6.1.2.1 Dose Escalation

None.

6.1.2.2 Dose Limiting Toxicity

As described in Section 2.3.1, toxicity from this radiolabeled drug comes from radioactive emissions and the mass dose of the nonradioactive carrier. Both the injected radioactivity and mass dose are many-fold lower than that required to cause toxicity.

6.1.2.3 Dose Modifications

The dose will not be modified by toxicity. Instead, the dose may be less than that prescribed, based on the PI's judgment of the magnitude of noise that will be acceptable in the brain and blood measurements.

6.1.2.4 Drug Administration

The radioligand will be injected intravenously and must be administered within four hours of its preparation.

6.2 PREPARATION/HANDLING/STORAGE/ACCOUNTABILITY

The radioligands are prepared by the NIMH radiochemistry laboratory and handled by the PET department radiopharmacy according to the associated INDs and SOPs. The radioligands have minimal storage because they must be injected within one hour of their preparation.

[figure not shown]
6.2.1 Acquisition and Accountability

The radioligand will be delivered by the NIMH radiochemistry laboratory to the PET Department's radiopharmacy. Acquisition and accountability are the responsibility of the NIMH radiochemistry laboratory.

[figure not shown]
Abbreviated Title: [¹⁸F]SF12051 in Healthy Subjects
Version Date: 12/05/23

6.2.2 Formulation, Appearance, Packaging, and Labeling

Each product will be formulated in sterile, apyrogenic saline containing 10% dehydrated alcohol in a single-use vial and labeled according to requirements for PET drug products described in USP Chapter <823>. The following label will be affixed directly to the vials prior to filling:

Two additional labels are placed on the outer lead shielding used to transport the vial to the radiopharmacy:

6.2.3 Product Storage and Stability

Products are stable at controlled room temperature for the four-hour expiration period and have no additional storage requirements. Product vials are expected to be single-use, but if the seal is broken and additional product must later be withdrawn, the same storage conditions and original expiration time would apply.

6.2.4 Preparation

Products are provided as sterile, directly injectable solution in a multi-dose vial. The PET radiopharmacist will aseptically remove from the multi-dose vial only the volume required for a participant dose. If necessary, this volume will be diluted with 0.9% normal saline, USP to 12 mL.

6.3 MEASURES TO MINIMIZE BIAS: RANDOMIZATION AND BLINDING

This study is neither randomized nor blinded.

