1.1 SYNOPSIS

| | |
|---|---|
| Title: | Assessment of [¹⁸ F]SF12051 for Imaging the 18-kDa Translocator Protein (TSPO) in Brain and Whole Body of Healthy Subjects |
| Study Description: | This study is intended to provide information on the novel [¹⁸ F]SF12051 radioligand and its ability to localize and measure TSPO in the brain and body of healthy individuals. |
| Objectives: | 
Primary Objective: To study the brain uptake of [¹⁸F]SF12051 and perform kinetic modeling of the [¹⁸F]SF12051 in the three different TSPO genotypes.
 
Secondary Objectives: To study the brain retest characteristics, biodistribution and dosimetry of [¹⁸F]SF12051 in healthy subjects.
 |
| Endpoints: | 
Primary Endpoint: The distribution volume of the radioligand and stability over time calculated with compartmental modeling, attention paid to differences in mean distribution volumes between TSPO genotypes for determining genotype sensitivity.
 
Secondary Endpoints: Retest variability and reliability and organ-time-activity curves to determine biodistribution and dosimetry.
 |
| Study Population: | Up to forty-five (45) healthy male and female volunteers (18 years and older) of the three different TSPO genotypes for brain and whole-body imaging. |
| Phase: | N/A |
| Description of Sites/Facilities | Screening and PET imaging will be performed at the NIH Clinical Center. |
| Enrolling Participants: | |
| Description of Study Intervention: | Arterial line, PET scan, and brain MRI scan for absolute quantification of TSPO. Blood drawn from all subjects to determine TSPO genotype. |
| Study Duration: | 3 years |
| Participant Duration: | 1-4 visits, 2-6 hours per visit. |

Abbreviated Title: [¹⁸F]SF12051 in Healthy Subjects

Version Date: 12/05/23

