5 STUDY POPULATION

5.1 INCLUSION CRITERIA

To be eligible to participate in this study, an individual must meet all of the following criteria:

1. Aged 18 years or older.
2. Healthy based on medical history, physical examination, and laboratory testing.
3. Able to provide informed consent.
4. Willing and able to complete all study procedures.
5. Have been screened for TSPO genotype under 01-M-0254 “The Evaluation of Patients with Mood and Anxiety Disorders and Healthy Participants”.
6. Have their radial artery pulse checked for the presence of adequate ulnar collateral flow and the absence of any metal or foreign objects in both wrists*.
7. Agree to adhere to the lifestyle considerations (see Section [5.4](#))

*Does not apply to Phase 1 and 3 participants as they will not have an arterial line.

Abbreviated Title: [¹⁸F]SF12051 in Healthy Subjects

Version Date: 12/05/23

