8.1.2 Screening activities performed after a consent for screening has been signed

Prior to consenting to this study, participants will have undergone an initial blood sample to determine TSPO genotype under protocol 01M0254 "The Evaluation of Participants with Mood and Anxiety Disorders and Healthy Volunteers", which allows for the sharing of collected data.

With the first visit under this protocol, all subjects will have a physical exam, EKG, and blood labs: CBC; acute care panel (Na, K, Cl, CO₂, creatinine, glucose, urea nitrogen); hepatic panel (alkaline phosphatase, ALT, AST, bilirubin total, and bilirubin direct); mineral panel (albumin, calcium, magnesium, phosphorus); prothrombin and partial prothrombin tests. Screening results will be reviewed by a clinically credentialed investigator before the subject undergoes any specific study procedures. Results of these tests will identify participants who should be excluded because of active medical problems or make participation in the protocol unsafe.

Subjects who successfully screen and are found eligible will be asked about their availability for scheduling of the PET scan(s) appointment. Occasionally, we have a last-minute cancellation due to scheduling conflicts, COVID exposure, etc. Given the complexities of arranging for the PET scan slot and synthesis of the ligand, we will inquire whether candidates have flexibility in their schedules to allow them to participate with less than 72 hours' notice. We will maintain a list of those who agree to be available on short notice so that we may contact them if we have a scheduled subject that needs to cancel. In the event that we schedule a participant with a 72-hour notice, we will provide an additional payment of \$250 if they come in and complete the PET scan.

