8.2.1 PET Procedures

Radioligand

[¹⁸F]SF12051 will be administered via an indwelling intravenous catheter over ~1 minute, within four hours after synthesis of the radioligand. The radioligand is stable during this period.

Insertion of the intravenous line

An intravenous line will be placed in the arm. The venous line will be used to inject the radioligand and will be removed at the end of the day. The IV line may be replaced if it fails to remain patent.

PET acquisition for brain and/or lung imaging

PET scans will be performed using a PET/CT or the HRRT. The choice of the scanner for a particular study will depend on scanner availability. Participants will be placed on the scanner bed with their head held firmly in place with a thermoplastic mask or a head holder fixed to the bed. A transmission scan will be performed before the PET scan to measure and correct for attenuation. Tracer infusions will be performed in the nuclear medicine department, while the subject is on the scanner bed.

After an intravenous bolus of about 5 mCi, arterial blood samples will be drawn from the arterial catheter during the PET scan. We will collect about 20-25 arterial samples. First, blood samples will be drawn every 15 seconds after injection for about 3 to 5 minutes, and then they will be collected every 5, 10, 15, or 30 minutes. The total amount of arterial blood will be about 100 mL. PET images of the brain will be acquired in three-dimensional mode with increased length of frame for a total of 120 minutes. The duration may be shortened on the basis of the results of time stability analysis.

At the end of the scans, the arterial and venous lines will be removed, and the subject will be instructed to void frequently to minimize radiation exposure.

PET acquisition for dosimetry

Whole body dosimetry scans will be performed with a PET/CT. The choice of the scanner for a particular study will depend on scanner availability. No arterial sampling will be done for dosimetry studies. Both a pre-injection transmission scan and a series of dynamic emission scans will be acquired. Each subject will be imaged in contiguous segments from the top of the head to a point below the gonads. To minimize extraneous motion, all subjects may wear a head-holding mask and will have their arms and abdomen wrapped with body-restraining sheets. This may add some additional discomfort. Venous samples up to 30 mL may be obtained

Abbreviated Title: [¹⁸F]SF12051 in Healthy Subjects

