9.2 SAMPLE SIZE DETERMINATION

To evaluate genotype sensitivity of [¹⁸F]SF12051 we calculated the percent difference in binding values necessary to differentiate between HABs, MABs and LABs. This was based on our previous results with [¹¹C]ER176 in healthy volunteers of different genotypes (Ikawa et al 2016). The mean V_T of HH subjects (HABs; n = 9) for whole brain was 4.5 mL/cm³ with a standard deviation of 1.4 mL/cm³. In addition, the V_T of HH subjects was 40% higher than the V_T of HL subjects. Assuming the same SD for [¹¹C]ER176 and [¹⁸F]SF12051, we can calculate how much of a difference in mean V_T can be detected between genotypes. Power analysis based on V_T of HH subjects from [¹¹C]PBR28 scans showed that with a sample size of 10 for each binder group, a power of 80% and alpha of 0.05 the percent difference to be detected from the mean value of a HAB is 40%. That is, the difference in mean V_T between HH and other genotypes should be >40% for it reach a statistical significance with a sample size of 10. Therefore, we require a recruitment of 34 in total for HABs, MABs and LABs under Phase 2 and 4 considering some withdrawals.

We wish to balance the number of subjects in the three TSPO genotypes: HAB, MAB, and LAB. Although all genotypes will be accepted during the initial scans, we will likely require specific genotypes toward the end of the scan, especially for the rare LABs. For this reason, we may select individuals based on TSPO genotype in order to have roughly equal number of subjects in the three groups.

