9.4.7 Sub-Group Analyses

The different genotype groups will be analyzed separately.

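### The plan has no step that keeps genotype from the analysts deriving V_T, although the primary endpoint compares mean V_T between genotypes

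*Combined protocol and SAP*

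**What the plan says.** On bias, section 6.3 consists of one sentence: "This study is neither randomized nor blinded". It makes no exception for image reading or kinetic analysis, and neither does section 9.4.1.

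Genotype is in the study's hands from the start:
- Inclusion criterion 5 (section 5.1): "Have been screened for TSPO genotype under 01-M-0254".
- Section 8.1.2: "Prior to consenting to this study, participants will have undergone an initial blood sample to determine TSPO genotype". The same section says that the source protocol permits the data to be shared.
- Section 9.2, on later recruitment: "we may select individuals based on TSPO genotype in order to have roughly equal number of subjects in the three groups".

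Genotype also organises the results. The synopsis (1.1) defines the primary endpoint as V_T and its stability, with "attention paid to differences in mean distribution volumes between TSPO genotypes for determining genotype sensitivity". Section 9.2 sizes the study on that comparison, and section 9.4.7 adds: "The different genotype groups will be analyzed separately".

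The route to V_T is described only in outline. The synopsis names compartmental modelling. Section 9.4.1 mentions PET–MRI coregistration to define regions and refers to identifiability and stability. It gives no model order, selection criterion, region method or rule for poor fits. On scan length, section 8.2.1 says: "The duration may be shortened on the basis of the results of time stability analysis", with no numerical criterion. Section 8.2.2 lets the blood-sampling plan change in the interest of data quality.

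**The concern.** V_T is calculated, but several of its inputs involve judgement: where regions are placed, which compartment model is kept, how the metabolite curve is fitted, which poor fits are dropped, and how much of the scan is analysed. If the person making those choices knows the genotype, the choices can differ between groups. The resulting offset then cannot be told apart from true genotype sensitivity, which is what the endpoint is meant to measure.

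Genotype cannot be randomised, so that half of section 6.3 is not at issue. Masking the analysts is possible, and the plan does not provide for it.

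The documents also create expectations in both directions. Section 2.1 predicts that the new ligand will behave like ER176 and so be sensitive to genotype. The hypotheses in sections 4.1 and 9.1 look for satisfactory performance whatever the genotype. An analyst could be drawn towards finding a difference or towards minimising one.

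**Working it through.** **Is the gap real?** Set side by side, sections 5.1, 8.1.2 and 9.2 put genotype in the study's hands before scanning. Section 1.1 makes genotype the comparison, and sections 6.3 and 9.4.1 contain no masking step. Section 2.1 does remark that genotyping could be left to the end, but as a practical advantage of a ligand such as ER176 in clinical protocols. It is not a procedure of this study.

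**Inputs for the illustration (section 9.2).** HAB mean V_T 4.5 mL/cm³, SD 1.4 mL/cm³, 10 per group, alpha 0.05 (taken as two-sided, since the plan does not say), and a detectable difference of 40% of the HAB mean, 0.40 × 4.5 = 1.8 mL/cm³. The mean and SD are given for ER176, although the power statement is credited to PBR28 scans. The same SD is assumed in every group.

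**Reproducing the plan's figure.** n per group = 2(z₀.₉₇₅ + z₀.₈₀)² × SD² / Δ² = 2 × (1.960 + 0.842)² × 1.4² / 1.8² = 9.5, rounded up to 10. The stated 10 per group reproduces. Power at n = 10 is 82.0% by the normal approximation and 77.6% by the exact two-sided t calculation. The t figure is the reference below.

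**Adding an offset.** The standard error of a difference in means is 1.4 × √(2/10) = 0.626, with 18 degrees of freedom. For a between-group offset b, the noncentrality is b/0.626 when there is no true difference, and (1.8 − b)/0.626 when the offset works against a true 40% difference. The rejection probability comes from the noncentral t distribution. The documents give no value for b, so the range is an assumption.

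| Assumed offset, % of HAB mean | b (mL/cm³) | Error rate, no true difference | Power, true 40% difference, offset against it |
|---|---|---|---|
| 0 | 0 | 5.0% | 77.6% |
| 5 | 0.225 | 6.3% | 66.3% |
| 10 | 0.450 | 10.5% | 53.2% |
| 15 | 0.675 | 17.5% | 39.8% |

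These figures show what an offset of each size would do to one pairwise comparison. They do not show that an offset exists.

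**The case against.** The strongest case on the other side is that this is a single-site, open, exploratory first-in-human tracer study with a computed endpoint. V_T uses a measured arterial input and MRI-based regions, and a model or duration rule applied alike to everyone leaves little room for a genotype-dependent shift. Section 9.4.2 plans only mean ± SD, so an error rate describes a test that is not named. Judging whether the model works in LABs is part of the purpose, and locking choices without genotype might obstruct that.

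Much of this stands as a limit on the size of the problem. It does not close the gap. No common rule is written down. An offset moves the group means whether or not a test is run, and section 9.2 does speak of reaching statistical significance. Time-stability can be judged on coded scans and then examined by genotype after V_T is locked, so evaluation in LABs is not blocked.

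Three stronger readings are tempting, and the documents support none of them:
- *That the modeller does see genotype.* No sentence says so. The cited sections concern eligibility, recruitment and grouping, and section 9.2 says only that selection by genotype may occur.
- *That the team has declared an expected order of HAB above MAB above LAB for this ligand.* Section 2.2.1 reports a preference for HABs, and section 9.2 a higher V_T in HH than HL subjects, but both describe ER176. The formal hypotheses point the other way.
- *That duration is chosen participant by participant.* Section 8.2.1 concerns shortening the acquisition after a time-stability analysis.

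**Conclusion.** The point holds as a missing safeguard. The study is declared unblinded, genotype is available before scanning, the primary endpoint compares genotypes, and no section masks the steps that produce V_T. Analyst choices can therefore be made with genotype known.

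The documents do not establish that bias will occur, which way it would run, or how large it would be. The table rests on assumed offsets, a common SD of 1.4 mL/cm³, 10 per group and a two-sided t-test that the plan does not name. Nobody should read from it that the trial's error rate is 17.5%, or that results will be pushed towards a genotype difference. What can be said is that an offset of 10% of the HAB mean, if present, would about double the nominal 5% error or cost about 24 percentage points of power (77.6% − 53.2%). This is a cheap improvement and not a fault that invalidates the design.

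**What to change.** In sections 6.3 and 9.4.1, state that:
1. Recruitment, including selection by genotype, and scanning remain open.
2. Analysts receive coded PET, MRI and plasma files without genotype.
3. Regions, compartment model, metabolite fit, fit exclusions and analysed duration are set by one written rule applied alike to all participants. Any time-stability analysis used to shorten acquisition is done on the coded scans.
4. Individual V_T values are locked, with a date, before genotype is linked.
5. Checks of identifiability and time-stability by genotype, including in LABs, follow the lock. Any later change of model is reported as post hoc, alongside the locked result.

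The cost is a coded hand-off within the existing team and a dated lock. The documents do not describe how the team is divided, so it is an assumption that someone other than the analyst can hold the key. Sample size, procedures and participant burden do not change. Masking will be imperfect, because low uptake may reveal LABs, so the common rule in step 3 matters as much as the coding. The safeguard has to be in place before analysis begins, since it cannot be restored after choices have been made with genotype in view.
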